Appendix E. Short Form (36) Health Survey (SF-36)

Your Health and Well-Being

This survey asks for your views about your health. This information will help keep track of how you feel and how well you are able to do your usual activities. *Thank you for completing this survey!*

For each of the following questions, please mark an in the one box that best describes your answer.

1. In general, would you say your health is:

Excellent	Very good	Good	Fair	Poor
 1	 2	 3	 4	 5

2. Compared to one year ago, how would you rate your health in general now?

Much better now than one year ago	Somewhat better now than one year ago	About the same as one year ago	Somewhat worse now than one year ago	Much worse now than one year ago
 1	 2	 3	 4	 5

3. The following questions are about activities you might do during a typical day. Does your health now limit you in these activities? If so, how much?

	Yes, limited a lot	Yes, limited a little	No, not limited at all
• Vigorous activities , such as running, lifting heavy objects, participating in strenuous sports	 1	 2	 3
• Moderate activities , such as moving a table, pushing a vacuum cleaner, bowling, or playing golf	 1	 2	 3
• Lifting or carrying groceries	 1	 2	 3
• Climbing several flights of stairs	 1	 2	 3
• Climbing one flight of stairs	 1	 2	 3
• Bending, kneeling, or stooping	 1	 2	 3
• Walking more than a mile	 1	 2	 3
• Walking several hundred yards	 1	 2	 3
• Walking one hundred yards	 1	 2	 3
• Bathing or dressing yourself	 1	 2	 3

4. During the past 4 weeks, how much of the time have you had any of the following problems with your work or other regular daily activities as a result of your physical health?

	All of the time	Most of the time	Some of the time	A little of the time	None of the time
• Cut down on the amount of time you spent on work or other activities	 1	 2	 3	 4	 5
• Accomplished less than you would like	 1	 2	 3	 4	 5
• Were limited in the kind of work or other activities	 1	 2	 3	 4	 5
• Had difficulty performing the work or other activities (for example, it took extra effort)	 1	 2	 3	 4	 5

5. During the past 4 weeks, how much of the time have you had any of the following problems with your work or other regular daily activities as a result of any emotional problems (such as feeling depressed or anxious)?

	All of the time	Most of the time	Some of the time	A little of the time	None of the time
• Cut down on the amount of time you spent on work or other activities	 1	 2	 3	 4	 5
• Accomplished less than you would like	 1	 2	 3	 4	 5
• Did work or other activities less carefully than usual	 1	 2	 3	 4	 5

6. During the past 4 weeks, to what extent has your physical health or emotional problems interfered with your normal social activities with family, friends, neighbors, or groups?

Not at all	Slightly	Moderately	Quite a bit	Extremely
 1	 2	 3	 4	 5

7. How much bodily pain have you had during the past 4 weeks?

None	Very mild	Mild	Moderate	Severe	Very Severe
 1	 2	 3	 4	 5	 6

8. During the past 4 weeks, how much did pain interfere with your normal work (including both work outside the home and housework)?

Not at all	A little bit	Moderately	Quite a bit	Extremely
 1	 2	 3	 4	 5

9. These questions are about how you feel and how things have been with you during the past 4 weeks. For each question, please give the one answer that comes closest to the way you have been feeling. How much of the time during the past 4 weeks...

	All of the time	Most of the time	Some of the time	A little of the time	None of the time
Did you feel full of life?	 1	 2	 3	 4	 5
Have you been very nervous?	 1	 2	 3	 4	 5
Have you felt so down in the dumps that nothing could cheer you up?	 1	 2	 3	 4	 5
Have you felt calm and peaceful?	 1	 2	 3	 4	 5
Did you have a lot of energy?	 1	 2	 3	 4	 5
Have you felt downhearted and depressed?	 1	 2	 3	 4	 5
Did you feel worn out?	 1	 2	 3	 4	 5
Have you been happy?	 1	 2	 3	 4	 5
Did you feel tired?	 1	 2	 3	 4	 5

10. During the past 4 weeks, how much of the time has your physical health or emotional problems interfered with your social activities (like visiting friends, relatives, etc.)?

	All of the time	Most of the time	Some of the time	A little of the time	None of the time
	 1	 2	 3	 4	 5

11. How TRUE or FALSE is each of the following statements for you?

Definitely true	Mostly true	Don't know	Mostly false	Definitely false
▼	▼	▼	▼	▼

1 I seem to get sick a little easier than other people..... 1 2 3 4 5

2 I am as healthy as anybody I know..... 1 2 3 4 5

3 I expect my health to get worse 1 2 3 4 5

4 My health is excellent..... 1 2 3 4 5

THANK YOU FOR COMPLETING THESE QUESTIONS!

Appendix F. EuroQol 5 dimension, 3 level quality of life questionnaire (EQ-5D-3L)

By placing a tick in one box in each group below, please indicate which statements best describe your own health state today.

Mobility

I have no problems in walking about

I have some problems in walking about

I am confined to bed

Self-Care

I have no problems with self-care

I have some problems washing or dressing myself

I am unable to wash or dress myself

Usual Activities (e.g. work, study, housework, family or leisure activities)

I have no problems with performing my usual activities

I have some problems with performing my usual activities

I am unable to perform my usual activities

Pain/Discomfort

I have no pain or discomfort

I have moderate pain or discomfort

I have extreme pain or discomfort

Anxiety/Depression

I am not anxious or depressed

[figure not shown]
I am moderately anxious or depressed

I am extremely anxious or depressed

To help people say how good or bad a health state is, we have drawn a scale (rather like a thermometer) on which the best state you can imagine is marked 100 and the worst state you can imagine is marked 0.

We would like you to indicate on this scale how good or bad your own health is today, in your opinion. Please do this by drawing a line from the box below to whichever point on the scale indicates how good or bad your health state is today.

Your own
health state
today

Appendix G. Work Productivity and Activity Impairment (WPAI)

Work Productivity and Activity Impairment Questionnaire: Rheumatoid arthritis V2.0 (WPAI:RA)

The following questions ask about the effect of your rheumatoid arthritis on your ability to work and perform normal daily activities. *Please fill in the blanks or circle a number, as indicated.*

1. Please check your current employment status.

 1	Full time (working for pay)
 2	Part time (working for pay)
 3	Volunteering
 4	Stopped working because of my RA
 5	Stopped working for other reasons
 6	Retired

*If your response is 1 or 2, continue the survey.
If your response is 3-6, skip to question 6.*

The next questions refer to the **past seven days**, not including today.

2. During the past seven days, how many hours did you miss from work because of problems associated with your rheumatoid arthritis? *Include hours you missed on sick days, times you went in late, left early, etc., because of your rheumatoid arthritis. Do not include time you missed to participate in this study.*

_____ HOURS

3. During the past seven days, how many hours did you miss from work because of any other reason, such as annual leave, holidays, time off to participate in this study?

_____ HOURS

[figure not shown]
4. During the past seven days, how many hours did you actually work?

_____ HOURS (If "0", skip to question 6.)

5. During the past seven days, how much did your rheumatoid arthritis affect your productivity while you were working?

Think about days you were limited in the amount or kind of work you could do, days you accomplished less than you would like, or days you could not do your work as carefully as usual. If rheumatoid arthritis affected your work only a little, choose a low number. Choose a high number if rheumatoid arthritis affected your work a great deal.

Consider only how much rheumatoid arthritis affected productivity while you were working.

[figure not shown]

CIRCLE A NUMBER

6. During the past seven days, how much did your rheumatoid arthritis problems affect your ability to perform your normal daily activities, other than work at a job?

By normal activities, we mean the usual activities you perform, such as working around the house, shopping, childcare, exercising, studying, etc. Think about times you were limited in the amount or kind of activities you could perform and times you accomplished less than you would like. If rheumatoid arthritis affected your activities only a little, choose a low number. Choose a high number if rheumatoid arthritis affected your activities a great deal.

Consider only how much rheumatoid arthritis affected your ability to perform your normal daily activities, other than work at a job.

CIRCLE A NUMBER

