4.0 Abstract

Title: Real-World Outcome of Rheumatoid Arthritis Patients in Korea on adalimumab (ROCKA Study).

Rationale and Background: Given the requirement to keep a balance between effectiveness and cost containment to ensure that the available health resources are used in a cost-effective manner, there is an increasing demand for real-world evidence (RWE) from policy makers, regulators, providers and payers in the region to optimize spending and patient outcomes.

So far, there are no data available regarding adalimumab's impact on patients' quality of life (QoL) and healthcare resource utilization (HCRU) in a realistic study design in Korea.

The goal of this study is to determine the QoL, HCRU and costs of the patients care in subjects with RA who are treated with adalimumab in Korea.

Results from study on the effect of adalimumab on Work Productivity and Activity Impairment (WPAI) scores and other Patient-Reported Outcomes (PROs) will be of interest to a variety of stakeholders in the healthcare system including patients, healthcare practitioners and payers in Korea.

Research Question and Objectives: The objective of this non-interventional, observational study is to assess the effect of adalimumab on health-related QoL and work productivity in patients with Rheumatoid Arthritis (RA) in Korea. Specifically, to achieve the above objective the following concrete steps will be taken:

1. Recruit investigators who are willing and able to recruit and follow new adalimumab users for 6 months follow-up
2. Collect the patients' clinical profile, patient-reported QoL, functioning, work productivity, treatment satisfaction and HCRU of RA patients at adalimumab initiation
3. Follow the patients initiating adalimumab for 24 weeks and identify the changes in clinical, economic, and PROs associated with adalimumab

Study Design: The study is designed as a prospective, observational study to assess the effect of adalimumab on health-related QoL and work productivity in patients with RA in Korea.

Note: This study is non-interventional and the subjects/investigators will follow the current clinical practice in each site and also the routine clinical follow up as determine by the treating physician.

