9.5 Study Size

Approximately 89 patients diagnosed with RA will be recruited. The sample size was calculated by assuming an alpha of 0.05 and a power of 0.80 in a one-sided test, $Z(1-\alpha) = 1.645$ and $Z(1-\beta) = 0.842$. As to the primary variable, assuming a mean Δ HAQ-DI of -0.21 and a standard deviation (SD) of 0.5, according to the formula, 36 subjects are required. Then, given the importance of the secondary endpoint (WPAI), an improvement of 9.9 ± 25 hours of work time lost (mean=9.9, SD=25) requires 40 subjects. However, we assume a 50% employment rate in the study population and a drop-out rate of 10%, eventually approximately 89 patients will be required ($40/0.5/(1-0.1) = 89$).

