9.7.2 Analyzable population

All subjects who received at least one dose of adalimumab during the study will be included. The main analysis will be conducted on the pooled population, where appropriate, with each individual country analyzed separately as supportive data.

9.7.3**Planned Methods of Statistical Analysis**

All statistical tests will be two-tailed with a significance level of 0.05. Descriptive statistics will be provided. Descriptive analysis will be conducted on all key parameters and presented as mean, standard deviation, minimum, maximum, and median when continuous and as “n” and percent when categorical. Change from adalimumab initiation to 24 weeks will be calculated and evaluated for significant improvements using paired t-tests / ANOVA for parametric and Wilcoxon signed-rank for non-parametric data. Analysis will be also be conducted by severity level (moderate vs severe), disease duration quartile (to compare to prior work) and up to two (2) other subgroups. Cochran-Armitage test of trends or other similar methods may be used to compare categories of subjects.

9.7.4**Primary Endpoint Analysis**

The primary endpoint variable will be the change in HAQ DI score at 24 weeks after the initiation of adalimumab (observed population).

The objective of the primary endpoint analysis will be to demonstrate that treatment with adalimumab improves functioning as measured by the HAQ DI in subjects with RA following treatment initiation. This change will be summarized as the mean and 95% confidence interval and will be tested with a paired t-test.

The primary analysis will be summarized as the mean and 95% confidence interval and will be tested with a paired t-test without adjusting for baseline disease severity. For sensitivity analysis, the mean change in HAQ DI at Week 24 will be analyzed using ANOVA adjusting for baseline disease severity.

9.7.5**Secondary Endpoint Analysis**

The main secondary endpoint variable will be the change in HAQ DI at 12 weeks after the initiation of adalimumab.

The objective of endpoint analysis will be to demonstrate that treatment with adalimumab improves functioning as measured by HAQ DI in subjects with RA compared to baseline.

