#### **Questions**

Q1 = currently employed

Q2 = hours missed due to specified problem

Q3 = hours missed other reasons

Q4 = hours actually worked

Q5 = degree problem affected productivity while working

Q6 = degree problem affected regular activities

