#### **5.4 Analysis Plan for Secondary Objectives**

In addition to HAQ DI score, the effect of adalimumab will also be assessed by the secondary outcome measures which are changes to the Short Form 36-Item Health Survey (SF-36) domain scores, EuroQol 5 dimension 3 level (EQ-5D-3L) index, WPAI outcomes, and Patient Treatment Satisfaction Questions at 12 and 24 weeks after the initiation of adalimumab in RA.

- As to the Short Form 36-Item Health Survey (SF-36) domain scores, the Excel Table 4 summarizes the changes in PCS T-score and MCS T-score at 12 and 24 weeks after the initiation of adalimumab; these changes will be summarized as the mean, SD, minimum, maximum, median, 95% confidence interval; and the mean change will be tested with paired t-tests with p-value listed in the table.
- As to the EuroQol 5 dimension 3 level quality of life questionnaire, the Excel Table 5 summarizes the changes in EQ-5D-3L index at 12 and 24 weeks after the initiation of adalimumab; these changes will be summarized as the mean, SD, minimum, maximum, median, 95% confidence interval; and the mean change will be tested with paired t-tests with p-value listed in the table.
- As to the WPAI outcomes, the Excel Table 6 summarizes the changes in percent overall work impairment and percent activity impairment at 12 and 24 weeks after the initiation of adalimumab; these changes will be summarized as the mean, SD, minimum, maximum, median, 95% confidence interval; and the mean change will be tested with paired t-tests with p-value listed in the table.
- Excel Table 7 describes the change in 4 patient satisfaction questions at weeks 12 and 24 after the initiation of adalimumab, in those patients continuing on adalimumab (responder population). These changes will be summarized as number and percentage of each response and compared with Wilcoxon signed rank test shown by p-value1. Satisfaction will also be dichotomized and analyzed over time with Cochran-Armitage test for trends shown by p-value2 in the table.

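### The WPAI work-impairment result covers only patients in paid work at both visits compared, and no analysis described in the SAP reports who stopped work because of RA or returned to it

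*Protocol*

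**What the plan says.** The protocol abstract (4.0) sets out to "assess the effect of adalimumab on health-related QoL and work productivity in patients with Rheumatoid Arthritis (RA) in Korea". Work productivity also fixes the sample size: Protocol 9.5 takes an improvement in "hours of work time lost (mean=9.9, SD=25) requires 40 subjects", then inflates for 50% employment and 10% drop-out to reach 89.

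The WPAI form in Appendix G has six employment options: full-time pay, part-time pay, volunteering, stopped because of RA, stopped for another reason, and retired. Options 1 and 2 continue. For the rest the instruction is "If your response is 3-6, skip to question 6", so Q2 to Q5 stay blank. Protocol Table 1 (9.1.1) schedules the form at baseline, Week 12, Week 24 and early termination.

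SAP 3.5.1 computes percent overall work impairment from Q2, Q4 and Q5. In its list of items the status question appears as "Q1 = currently employed". In SAP 5.4, "the Excel Table 6 summarizes the changes in percent overall work impairment and percent activity impairment at 12 and 24 weeks", with paired t-tests. Protocol 9.7.9 and SAP 3.5.5 allow only item-level imputation under the developers' rules, and SAP 3.5.5 bases the analysis on available data. Neither the baseline characteristics in SAP 5.2 nor the table list in SAP 6 includes employment status.

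**The concern.** Whether a patient enters the work analysis depends on the patient's work outcome. Someone employed at baseline who has given up work because of RA by Week 24 has the worst work result the form can record, yet has no change score. Someone who had given up work because of RA and is back in paid work has the best, and has none either. Protocol 7.0 expects the work-productivity data to support the case for keeping the current patient co-payment ratio. For that use, job loss and return to work are part of the question, and the planned output does not mention them. Percent activity impairment (Q6) includes these patients, but the item asks about activities other than paid work.

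**Working it through.** **1. Who has a change score.** No single sentence states the restriction. It follows from four parts of the plan:
- Appendix G: status 3 to 6 leaves Q2 to Q5 blank.
- SAP 3.5.1: score = Q2/(Q2+Q4) + [1 - Q2/(Q2+Q4)] x Q5/10, so Q2, Q4 and Q5 are all needed.
- SAP 5.4: the paired t-test needs a score at baseline and at the follow-up visit.
- Protocol 9.7.9 and SAP 3.5.5: a missing score is not filled in.

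A patient must therefore be in paid work at both visits compared, and the Week 12 and Week 24 sets can differ. This is an upper limit. A paid worker who worked 0 hours also skips Q5, and the SAP has no rule for that case.

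**2. The plan's own count.** With the values in Protocol 9.5 (one-sided z 1.645, power z 0.842, mean 9.9, SD 25):
- n = (25 x (1.645 + 0.842) / 9.9)² = 6.280² = 39.4, rounded up to 40.
- N = 40 / 0.5 / 0.9 = 88.9, rounded up to 89.
- Back again: 89 x 0.9 x 0.5 = 40.05.

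Both stated figures reproduce. The plan uses one employment rate and no transitions, so 40 pairs are reached only if every completer employed at baseline is still employed at Week 24. Returners add no pairs, because they have no baseline score. The documents give no leaving rate. If 5%, 10% or 20% of the 40 leave paid work for any reason, 38, 36 or 32 pairs remain. Power by the same normal approximation falls from 80.5% to 78.7%, 76.8% or 72.4% one-sided. It falls from 70.7% to 68.5%, 66.1% or 61.0% under the two-tailed test of Protocol 9.7.3. The mismatch between one-sided sizing and two-tailed testing is a separate matter.

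**3. Effect on the mean.** Every value here is assumed, in percentage points of overall work impairment (negative is improvement). Stayers change by -15. Leavers go from 60 to 100 (+40). Returners go from 100 to 30 (-70).

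| Leavers | Returners | Calculation | Mean |
|---|---|---|---|
| not counted | not counted | planned analysis | -15.0 |
| 2 of 40 | 0 | (38 x -15 + 2 x 40)/40 | -12.25 |
| 4 of 40 | 0 | (36 x -15 + 4 x 40)/40 | -9.5 |
| 2 | 2 | (38 x -15 + 2 x 40 + 2 x -70)/42 | -15.0 |
| 4 | 4 | (36 x -15 + 4 x 40 + 4 x -70)/44 | -15.0 |

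If returners go only from 100 to 60 (-40), the last row becomes (-540 + 160 - 160)/44 = -12.3. More returners than leavers would take the mean beyond -15. Each omission matters, and the two pull in opposite directions.

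**4. Why the sensitivity analysis must be bounded.** If RA-related stopping scored 100% at every visit where it was ticked, patients out of work throughout would enter as 100 to 100, a change of zero. Adding 10 such patients (assumed) to the last table row gives -660/54 = -12.2 instead of -15.0, although nobody's work status has changed. Requiring paid work at one or both of the visits compared avoids this dilution.

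**The case against.** The strongest reply is that work scores for workers only are how the questionnaire is built. Protocol 9.7.1 commits to the developers' scoring, and Protocol 9.5 openly sizes for an employed subset. SAP 3.5.5 also requires the number of patients with missing data to be reported for each variable. All of that stands: the restriction is neither hidden nor a scoring error. But a missing-data count would not separate retirement from giving up work because of RA, and it would not show returns.

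Second, work is not wholly absent elsewhere. SF-36 questions 4 and 8 and the EQ-5D usual-activities item mention work, and every patient is given them. They feed broader health scores, though, and do not measure productivity or employment.

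Third, the full table shells are in a separate workbook that is not part of the documents. An employment table there cannot be excluded, but SAP 5.4 names only two WPAI scores for its table.

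Three stronger readings are tempting and not supported. A reader might infer that the planned mean is biased in favour of adalimumab; that follows only if returners are ignored. A reader might infer that the study can say nothing about work productivity; it can state the change among patients in paid work at both visits. A reader might infer that the SAP collapses the six-option status item to yes or no; the entry is a label in a list, Q1 enters no formula, and no recode is specified.

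**Conclusion.** The point holds as a gap in analysis and labelling. The WPAI work result describes, at most, patients in paid work at baseline and at the visit analysed. The plan describes no analysis of RA-related stopping or of return to paid work, although both can be read from data it collects. Net direction and size are unknown. The figures of -9.5 (4 leavers of 40, no returners) and -15.0 (4 of each) show only how far the answer depends on rates that the documents do not give, and they rest on the assumed scores in the table. WPAI is a secondary endpoint and the primary HAQ DI analysis is unaffected. The change is still worth making, because work productivity is a stated objective and sets the sample size.

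**What to change.** In SAP 5.4 and its WPAI table (Excel Table 6):

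1. Add a shift table of the six-category status item from baseline to Week 12 and to Week 24. Give counts of RA-related stopping among those employed at baseline, and of returns to paid work among those who had stopped because of RA.
2. Label the paired t-test as applying to patients in paid work at both visits, and limit its conclusion to them.
3. Add a sensitivity analysis that scores RA-related stopping as 100% overall work impairment, restricted to patients in paid work at one or both of the two visits compared. Leavers and returners then both count, and patients out of work throughout do not dilute the mean.

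SAP 5.1 allows the tables to be modified in the light of the results, so these additions should be written in before the WPAI results are seen.

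The cost is SAP wording, one table and one extra run on data already collected. No visit, questionnaire or clinical procedure changes. The downside is that scoring job loss as 100% is a convention, so it should remain a sensitivity analysis, and its result may be less favourable than the planned one.
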